2.3 Patient Numbering

Each patient will be uniquely identified in the study by a combination of the site number and screening number. The site number will be assigned by the coordinating site. The screening number will be assigned sequentially.

3. ADVERSE AND SERIOUS ADVERSE EVENTS

3.1 Adverse Events Definition

An AE is any untoward medical occurrence in a human subject, including any abnormal sign (for example, abnormal physical exam or laboratory finding), symptom, or disease temporally associated with the subject's participation in the research.

3.2 Serious Adverse Event (SAE) Definition

An SAE is any untoward medical occurrence related to study participation that:

1. Results in death.
2. Is life-threatening (an event which places the patient at immediate risk of death from the event as it occurred. It does not include an event that had it occurred in a more severe form might have caused death).
3. Requires in-patient hospitalization or prolongation of existing hospitalization.
4. Results in persistent or significant disability or incapacity.
5. Is a congenital abnormality or birth defect.
6. An important medical event that may not be immediately life-threatening or result in death or hospitalization but may jeopardize the patient and may require intervention to prevent one of the other outcomes listed in the definition above (e.g. events include allergic bronchospasm requiring intensive treatment in an emergency room or at home, blood dyscrasias, convulsions, or the development of drug dependency or abuse).

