3.3 Collecting and Reviewing Adverse Event and Outcome Information

During follow-up visits, whether in person or via telephone, the subjects will be asked about medically relevant changes in their health since the previous visit including hospitalization, and whether those hospitalizations were related to cardiovascular health.

In addition to patient observations, relevant events and outcomes will be documented from any clinically relevant laboratory findings, physical examination findings, ECG changes, or other findings found in the electronic medical record. The study team will record such information on Case Report Forms (CRFs) for each study visit and enter the information into the data collection system (RedCap) throughout the study. A checklist of potential adverse reactions to the imaging agent will be used to track all adverse events related to imaging agent for each subject. According to the package insert for Technetium Pyrophosphate, common side effects include flushing, hypotension, fever chills, nausea, vomiting and dizziness, as well as hypersensitivity reactions such as itching and various skin rashes

The study team will record AE information for start dates/times occurring any time after informed consent is obtained until 48 hours after the time of imaging agent infusion.

To assess relationship of an event to study procedure, the following guidelines are used:

- Unrelated
- Unlikely to be related
- Possibly related
- Probably related
- Definitely related

All adverse events must have their relationship to study participation, expectedness and severity of the event assessed by a qualified investigator, upon reporting of the event. These determinations will be made according to the professional opinion of the investigator using the package insert of the imaging agent and the investigators assessment will be entered into the Redcap data collection software by research staff.

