3.5 Adverse Event Reporting

3.5.1 Reporting to the Sponsor

Each participating investigator must report every serious adverse event (SAE) to the IND sponsor at Columbia University Medical Center as soon as possible, but no later than 48 hours after becoming aware of the event via phone, email or facsimile, and must complete the new SAE field on the Redcap database as soon as possible but no later than 48 hours after becoming aware of the event. The site investigator must document the time of his or her awareness of the SAE in an email or facsimile to:

Name: [name]
[contact]
[contact]
Email: [contact]

The participating investigator must also provide follow-up information on the SAE once new or updated information is available. The follow-up information must be added to the Redcap SAE field, as a follow-up to the initial entry.

Non-serious adverse events will be reported to the IND sponsor at Columbia University Medical Center on the Adverse Event Form through ordinary electronic data capture at RedCap. All non-serious entries related to adverse events must be completed by the participating investigator within 5 business days.

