3.5.3 Reporting to the FDA

Suspected Adverse Reaction:

In accordance with 21 CFR 312.32(a), a suspected adverse reaction (SAR) means any adverse event for which there is a reasonable possibility that the drug caused the adverse event.

The IND Sponsor will be responsible for all communication with the FDA and will report to the FDA, any adverse event that is serious, unexpected and for which there is reasonable possibility that the drug caused the adverse event. These must be reported to the FDA as soon as possible, but no later than 15

calendar days after the Sponsor determines that the information qualifies for reporting. Any fatal or life-threatening SARs will be reported to the FDA as soon as possible, but no later than 7 calendar days after the Sponsor determines that the information qualifies for such reporting.

All other serious adverse events will be included in the IND annual reports that are to be submitted to the FDA within 60 days of the anniversary date of the IND each year.

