Form Completed by: _____ Investigator's Signature: _____

10. For out-of hospital death (including those that occur in the ER): list the location (including city and state), social setting, and type and duration of symptoms. Specific symptoms of interest include: angina; pain or discomfort in the chest, left arm, shoulder or jaw; increased fatigue or tiredness; shortness of breath; dizziness; palpitations; paralysis; loss of speech.

Be as specific as possible when reporting information such as the precise location of death, when the patient was last seen alive, who last saw the patient alive, and location of those final sightings in relation to the site where the participant died. The Central Study Coordinator may request any information about the patient's treatment during the last six months of life. If you need more space, write on the back of this form.

Part D. SAE Summary

11. Outcomes: Indicate any of the specific following conditions that occurred as part of this experience (mark all that apply).

- Arrhythmia, atrial fibrillation or flutter
- Heart Attack
- Stroke or TIA
- New or worsening Heart Failure/Heart Failure Exacerbation
- Chest pain (hospitalized only)
- Kidney Failure / Dialysis
- GI Bleeding
- Infection
- Arrhythmia, Ventricular
- Amputation of part of leg, including toes, because of poor circulation/gangrene
- Other problems with heart, brain or circulation (specify: _____)

Form Completed by: _____ Investigator's Signature: _____

Visit: **ALL** Date of Visit: ____ / ____ / ____

Subject ID: ____

12. Was this event caused or worsened by enrollment in the study or any of its procedures?

- No
- Possibly
- Definitely

If possible or definitely, why?

13. Investigator Signature (Indicate when reviewed and approved by Clinic PI)

Signature: _____ Date: ____ / ____ / ____

Form Completed by: _____ Investigator's Signature: _____

Adverse Events Log

Protocol: _____	IRB #: _____
Principal Investigator: _____	Site: _____
Subject ID #: _____	

Adverse Event (Please use medical terminology)	Serious Adverse Event	Date Site Became Aware	Start Date	End Date - OR - Continuing	Severity (Grade)	Relatedness to Study Participation	Outcome	Report to External Entities (If applicable)	PI Initial & Date

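### Section 3.2 makes relatedness a condition of being an SAE, so a serious event the site calls unrelated loses SAE status and the 48-hour sponsor report, in conflict with 3.3 and the report forms

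*Combined protocol and SAP*

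**What the plan says.** Section 3.1 defines an adverse event by timing alone: it covers any abnormal sign, "symptom, or disease temporally associated with the subject's participation in the research". Section 3.2 then narrows the serious category by cause: "An SAE is any untoward medical occurrence related to study participation that" meets one of six listed outcomes, among them death and hospitalisation.

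Section 3.3 has relatedness judged for every event when it is reported: "All adverse events must have their relationship to study participation, expectedness and severity of the event assessed by a qualified investigator". Its five-step scale starts at 'Unrelated'. It records adverse events from consent until 48 hours after the tracer is given.

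Section 3.5.1 states: "Each participating investigator must report every serious adverse event (SAE) to the IND sponsor", with a limit of 48 hours from awareness. Non-serious events go to the same sponsor through the RedCap database within 5 business days. Section 3.5.3 has the sponsor decide on expedited FDA reports and adds: "All other serious adverse events will be included in the IND annual reports".

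In Appendix 4, item 12 of the Serious Adverse Event form asks: "Was this event caused or worsened by enrollment in the study or any of its procedures", and one permitted answer is 'No'. The Adverse Events Log has one column for serious (yes or no, with yes leading to the SAE form) and a separate column for relatedness that includes 'Not Related'.

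**The concern.** Whether an event is serious and whether the study caused it are different questions, and the second is the one on which a site can be wrong. Under 3.2 the site must answer it first, because the answer decides whether the event is an SAE at all. The site's causality call therefore comes before the sponsor's own determination under 3.5.3 and controls how fast, and under what label, the event arrives.

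Participants are aged 60 or over with heart failure. Several reactions for which 3.4 stops the scan, such as hypotension, shortness of breath and tachycardia, can readily be put down to that disease. Two tracers may be used. Ambiguous events after injection are the ones for which review pooled across sites and tracers is most useful, and they are the ones most likely to lose the SAE label.

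**Working it through.** No figure in the plan bears on this point, so the check is a comparison of the text followed by a rough size.

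**1. How each place treats relatedness**

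| Place | Role of relatedness |
|---|---|
| 3.1 | None; timing only |
| 3.2 | Condition for being an SAE |
| 3.3 | Assessed for all adverse events upon reporting; 'Unrelated' allowed |
| SAE form, item 12 | Answered on an SAE already being reported; 'No' allowed |
| Adverse Events Log | Column separate from the serious yes/no column |
| 3.5.3 | One of three tests (serious, unexpected, possibly drug-caused) applied by the sponsor |

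Section 3.2 is the exception. If it is applied literally, the 'Unrelated' grade and the 'No' answer can never be used for an SAE.

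**2. Route of a death or hospitalisation the site calls unrelated, with onset inside the recording window**

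- Under 3.1 it is an adverse event.
- Under 3.2 it is not an SAE, so the 48-hour report is not triggered and no SAE form is required.
- The only other route in 3.5.1 is the one for non-serious events. Read strictly, a death does not fit there either. At best it arrives within 5 business days, normally 7 calendar days, instead of 2 days.
- It does not enter the SAE count for the IND annual report.

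**3. The same event with onset after the window**

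Adverse event recording under 3.3 has ended. The event is collected, whatever its cause, on the 6- or 12-month follow-up form and then entered in the shared database within five days of the visit (section 4.5). Taking 6 months as 26 weeks and using the full 2-week visit tolerance, an event soon after injection could wait (26 + 2) × 7 + 5 = 201 days.

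**4. Size**

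- Participants: 800 (section 2.1.7).
- Time at risk after injection: 48 hours = 2 days (section 3.3).
- Hospitalisation rate: not given in the documents; assumed 0.5 to 1.0 per person-year.

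Expected number = 800 × (2/365) × rate:

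- At 0.5: 800 × 2/365 × 0.5 = 2.2
- At 1.0: 800 × 2/365 × 1.0 = 4.4

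This counts all hospitalisations in those two days. Those judged unrelated are a subset.

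**The case against.** A reader might infer that an event called unrelated never reaches the IND sponsor. The documents do not support that. Inside the recording window it is still an adverse event under 3.1, and 3.5.1 sends events not handled as SAEs to the same sponsor. The Adverse Events Log carries severity grades for life-threatening events and death beside the 'Not Related' box, so such an entry would be visible. The imaging sheet has tick boxes for hypotension, palpitations, tachycardia and shortness of breath. Deaths and hospitalisations of any cause are collected at 6 and 12 months, and the lead site's monitoring under 4.7 looks for unreported events.

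It also goes too far to say that the sponsor cannot make its own determination. The expedited test in 3.5.3 starts from any adverse event that is serious, not from the 3.2 list, so the sponsor can apply it to the entries it receives. What remains is that these arrive later and under a non-serious heading.

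Nor do the reporting sections plainly contradict 3.2. 'Every' SAE in 3.5.1 uses the defined term. The remainder sent to the annual report under 3.5.3 makes sense under 3.2 as related events that were expected, or that came from a procedure and not the drug. The textual conflict is with 3.3, the SAE form and the log.

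A larger size might be read from the whole recording period: 28 days from screening to baseline plus 2 days gives 800 × 30/365 × (0.5 to 1.0) = 33 to 66 hospitalisations. But 28 of those 30 days precede any tracer, so this does not measure what is lost on tracer safety.

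Finally, the SAE form itself has no relatedness gate, so some sites may report unrelated serious events regardless. That would soften the effect but make reporting differ between sites.

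**Conclusion.** The point holds as an internal conflict with a safety consequence. A serious event the site calls unrelated loses the 48-hour report, the SAE form and its place in the annual SAE count, and the site's view on cause is applied before the sponsor's. The event is delayed and misclassified; the text does not show that it is withheld altogether.

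The conclusion rests on the wording of 3.2 against 3.3 and the forms, not on the size estimate. Under the assumed rates, 2 to 4 hospitalisations within 48 hours after injection is an upper figure for that period. The number is small, but few events are needed to matter in judging the safety of an injected agent. The change should be made.

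**What to change.** - In 3.2, strike the words that require a relation to study participation, so that any adverse event meeting a seriousness criterion is an SAE. Keep relatedness as the separate 3.3 assessment that drives 3.5.2 and 3.5.3.
- Apply this regardless of relatedness within the adverse event recording period. State that serious events with later onset that are judged related remain reportable as they are now. Section 3.2 currently has no time limit, and restricting SAEs to the recording period would drop related events starting more than 48 hours after the tracer is given.
- Reconcile that 48-hour window with the adverse events review that the visit schedules place at 6 and 12 months.

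The existing forms and database fields already support this, so the cost is a short amendment to sections 3.2 and 3.3 and some more SAE forms for unrelated events: at most the 2 to 4 above for the two days after injection. Over the whole window from consent, the same assumed rates put the limit at 33 to 66 across the study, and only if every participant waited the full four weeks for baseline and every event was judged unrelated.

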3.3 Collecting and Reviewing Adverse Event and Outcome Information

During follow-up visits, whether in person or via telephone, the subjects will be asked about medically relevant changes in their health since the previous visit including hospitalization, and whether those hospitalizations were related to cardiovascular health.

In addition to patient observations, relevant events and outcomes will be documented from any clinically relevant laboratory findings, physical examination findings, ECG changes, or other findings found in the electronic medical record. The study team will record such information on Case Report Forms (CRFs) for each study visit and enter the information into the data collection system (RedCap) throughout the study. A checklist of potential adverse reactions to the imaging agent will be used to track all adverse events related to imaging agent for each subject. According to the package insert for Technetium Pyrophosphate, common side effects include flushing, hypotension, fever chills, nausea, vomiting and dizziness, as well as hypersensitivity reactions such as itching and various skin rashes

The study team will record AE information for start dates/times occurring any time after informed consent is obtained until 48 hours after the time of imaging agent infusion.

To assess relationship of an event to study procedure, the following guidelines are used:

- Unrelated
- Unlikely to be related
- Possibly related
- Probably related
- Definitely related

All adverse events must have their relationship to study participation, expectedness and severity of the event assessed by a qualified investigator, upon reporting of the event. These determinations will be made according to the professional opinion of the investigator using the package insert of the imaging agent and the investigators assessment will be entered into the Redcap data collection software by research staff.

3.4 Stopping Study Procedure Due to Adverse Event

In the ordinary ongoing off-label use of this procedure there have been no reports of serious adverse reactions. Nevertheless, the injection and scan procedure will be stopped and the results will be marked as incomplete if there are any adverse reactions during its administration as part of this study. The adverse reactions that will lead the investigators to stop the cardiac amyloid scintigraphy scanning portion of the study procedures include but are not limited to the events listed in the package insert: hypotension, fever, chills, nausea, vomiting and dizziness, as well as hypersensitivity reactions such as itching and various skin rashes.

The scan will also be stopped in cases of severe cardiac symptomology such as: chest pain, shortness of breath, palpitations, tachycardia. In such cases, other study procedures may be continued.

In addition, subjects will be asked to contact the investigators if any additional adverse or allergic reactions are noted within the first 24 hours following the injection. If any such events are reported, the principal investigator will determine if they are potentially related to the administration of the imaging agent. Appropriate clinical care will be advised for any events determined by the investigator to be related to the scanning injection, and information about the reactions will be reported as described below.

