Six-Minute Walk Test		X	X	X
Short Physical Performance Battery		X	X	X
QoL Questionnaires		X	X	X
Health Literacy Questionnaire		X		
Echocardiogram		X		X
^{99m} Tc-PYP Scintigraphy**		X		
Phone Call Follow-Up [¶]			X	X

* Follow-up visits are to be conducted on subjects who test positive to the Cardiac Amyloid Scintigraphy scan and/or are carrier of the V122I mutation. Window for the 6-month visit is ±2 weeks and for the 12-month visit is ±4 weeks.

† Height measured only at baseline visit. Subjects with weight >350 lb will not participate in the study.

‡ Includes BNP, NT-proBNP, galectin-3, troponin I and T.

§ Includes Vitamin A and RBP4 in on site spot urine.

¶ For participants with no TTR CA, a phone call follow-up will be conducted instead.

**In the event that PYP is unavailable due to supply shortage, the investigator has the option of using HDP until PYP becomes available again to ensure study continuation per FDA.

For every study visit, a checklist will be used to help ensure completion of all the study procedures. The checklist is also a guide that suggests the order in which the assessments should be performed (See [Appendix 3](#)).

TABLE OF CONTENTS

STUDY SYNOPSIS.....	2
LIST OF ABBREVIATIONS AND DEFINITIONS OF TERMS.....	9
1. INTRODUCTION	10
1.1 Background and Rationale	10
1.1.1 Transthyretin Biology	10
1.1.2 Transthyretin-mediated amyloidosis definition	10
1.1.3 Pathogenesis and Outcome.....	11
1.1.4 ATTR-CM and Heart Failure	11
1.2 ATTR-CM Population Burden.....	13
1.2.1 ATTR amyloid is an under-recognized cause of heart failure	13
1.2.2 Are Hispanics affected by TTR-CA?	14
1.2.3 TTR-CA from mutant protein has more severe phenotype than wild type	14
1.3 Natural History of Transthyretin Cardiac Amyloidosis	15
1.3.1 Clinical Characteristics and Outcome in ATTR-CA in TRACS	15
1.3.2 Predictors of Mortality	16
1.4 Therapeutic Options.....	17
1.4.1 Novel Therapies Require Early Identification of Affected Individuals	17
1.4.2 Tc-PYP & Tc-HMDP can detect TTR-CA without the need for an amyloid biopsy	
18	
1.4.3 Myocardial retention of Tc99-PYP is prognostic in TTR-CA	18

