2.1.5 Study Procedures

The timing of all procedures in this study is outlined in Table 4. Eligible patients will be identified. Patients who are interested in the study will have a screening visit to evaluate for eligibility and obtain informed consent. If patients qualify for study and do consent they will have their study visit within 4 weeks of screening. At that visit they will have all of the following testing done.

Table 4. Study Procedures

Procedure	Screening	Baseline	6 Months* (± 2 weeks)	12 Months* (± 4 weeks)
Informed Consent	X			
Inclusion and Exclusion Criteria	X			
Baseline History		X		
Height and weight [†]		X	X	X
Vitals Signs		X	X	X
Medications		X	X	X
Clinical Examination		X	X	X
Adverse Events Review		X	X	X
Electrocardiogram		X	X	X
Laboratory Analysis				
Basic Metabolic Panel		X	X	X
Hepatic Function Panel		X	X	X
Cardiac Biomarkers [‡]		X	X	X
Vitamin A/RBP4 in plasma/urine [§]		X	X	X

Prealbumin		X	X	X
TTR Kinetic Stability		X		X
TTR Gene Sequencing		X		
Ancestry Analysis		X		
Six-Minute Walk Test		X	X	X
Short Physical Performance Battery		X	X	X
QoL Questionnaires		X	X	X
Health Literacy Questionnaire		X		
Echocardiogram		X		X
^{99m} Tc-PYP Scintigraphy**		X		
Phone call follow-up [†]			X	X

* Follow-up visits are to be conducted on subjects who test positive to the cardiac amyloid nuclear scan and/or are carrier of the V122I mutation. Window for the 6-month visit is ± 2 weeks and for the 12-month visit is ± 4 weeks.

[†] Height measured only at baseline visit.

[‡] Includes BNP, NT-proBNP, galectin-3, troponin I and T.

[§] Includes Vitamin A and RBP4 in on site spot urine.

**In the event that PYP is unavailable due to supply shortage, the investigator has the option of using HDP until PYP becomes available again to ensure study continuation per FDA.

¶ For participants with no TTR CA, a phone call follow-up will be conducted instead.

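### Adverse events count if they start within 48 hours of the tracer, but participants are asked to call about reactions in the first 24 hours, so capture on the second day is unprompted.

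*Combined protocol and SAP*

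**What the plan says.** Section 3.3 defines which adverse events are recorded: those with a start date or time from informed consent "until 48 hours after the time of imaging agent infusion".

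Section 3.4, which deals mainly with stopping the injection and scan, sets out what participants are to do afterwards: "subjects will be asked to contact the investigators if any additional adverse or allergic reactions" "are noted within the first 24 hours following the injection". The principal investigator then judges whether the event may be related to the tracer.

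Table 4 in section 2.1.5, like the schedule in the synopsis, marks "Adverse Events Review" at baseline, 6 months and 12 months. The footnote sets the timing: "Window for the 6-month visit is ±2 weeks and for the 12-month visit is ±4 weeks". In-person follow-up is for participants with a positive scan or the V122I mutation. For the rest the footnote reads: "For participants with no TTR CA, a phone call follow-up will be conducted instead".

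Section 3.3 also gives two later sources. At follow-up, in person or by telephone, "the subjects will be asked about medically relevant changes in their health since the previous visit including hospitalization". Events are also taken from laboratory, examination and ECG findings "or other findings found in the electronic medical record".

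**The concern.** Two adjacent sections give different periods for the same agent, and neither explains the difference. A participant who follows section 3.4 as written has no prompt to call about a rash that starts at hour 30, yet section 3.3 tells the team to record it.

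What is at stake is safety ascertainment for an agent used under an IND. The reporting duties in section 3.5 depend on the site learning of the event. Section 3.3 has relatedness, expectedness and severity assessed when the event is reported, so a second-day reaction first mentioned at the 6-month contact is judged about half a year late and from recall. A mild reaction may never be mentioned.

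**Working it through.** The plan states no figure to reproduce here. The check sets the passages side by side, with simple arithmetic.

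**Inputs**
- Recording window: onset up to 48 h after the tracer (section 3.3).
- Period for which participants are asked to call: first 24 h (section 3.4).
- Scan: about 3 h after injection (section 2.1.5.2). The reaction checklist is on the imaging sheet for that visit (Appendix 4).
- Next scheduled contact: 6 months ±2 weeks (schedule footnote).
- Expected non-amyloid participants: 640 to 720 of the planned 800 (section 2.1.7).

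**Step 1. Length of the unprompted period.** 48 h − 24 h = 24 h, and 24/48 = 50% of the post-injection recording window.

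**Step 2. Time to the next scheduled contact.** Taking 6 months as 182 days (an assumption), 182 days less 14 days is 168 days, and 182 days plus 14 days is 196 days, that is, 24 to 28 weeks.

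**Step 3. Size of the group without visits.** Of the planned 800 participants, 640 are 80% and 720 are 90%. This is an upper bound on the phone-only share, because scan-negative V122I carriers are non-amyloid but are given visits. The documents do not give their number.

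**Step 4. Follow a reaction that starts at hour 30 through each route.**

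| Route | Does it reach hour 30? |
|---|---|
| Checklist on the imaging sheet | No; it belongs to the scan visit |
| Participant call under section 3.4 | Not prompted; a call is not refused |
| 6-month visit (scan-positive or carrier) | Yes, by recall, through the adverse event review and the question on health since the last visit |
| 6-month call (the rest) | Partly. Its purpose is limited to vital status and hospitalizations (section 2.1.5.8). The case report form for the call adds ER visits, ambulatory procedures and COVID-19 but has no item on tracer reactions. Section 3.3 asks more broadly about changes in health |
| Medical record | Only if the event led to care or a chart entry |

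An hour-30 event that led to an admission or an ER visit can therefore be found and dated later. An itch or rash that settled at home has no prompt at the time. In the phone-only group it depends on the participant raising it in answer to a general question months later. Section 3.3 itself lists itching and skin rashes among the known reactions, so this is the kind of event concerned.

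**The case against.** The strongest reply is that the two sections do different jobs. Section 3.4 tells participants when to call so that relatedness can be judged and care advised; section 3.3 governs data recording. A 24-hour request inside a 48-hour onset window is not in itself a contradiction, and section 3.4 does not turn away later reports. It also says that ordinary use of the procedure has produced no reports of serious reactions. All of this is fair. What it leaves unanswered is how second-day events are meant to reach the team.

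A reader might infer three stronger things, and the documents support none of them.

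- **That the second day goes unobserved.** It does not. Section 3.3 asks at follow-up, including by telephone, about health since the last visit, and draws on the medical record. The phone form collects dated hospitalizations and ER visits and allows chart review.
- **That the 6- and 12-month adverse event reviews in Table 4 conflict with the 48-hour window because it has closed by then.** The window is defined by when the event starts, with no deadline for learning of it. The adverse event log has separate columns for the start date and the date the site became aware. A later review can properly record an event that began within the 48 hours.
- **That a 48-hour adverse event rate is biased downward.** Section 2.1.8 defines no such rate, so there is no planned estimate to bias.

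It is also fair to say that the consent form or a take-home sheet may carry a different instruction. The consent pages are not in the file, so this can be neither confirmed nor ruled out.

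**Conclusion.** The point holds as a limited gap in safety ascertainment. Prompted reporting covers 24 of the 48 hours in which events count, and no contact is scheduled from the scan visit until about 24 to 28 weeks later. Mild delayed reactions are likely to be under-recorded or assessed months late, chiefly in participants followed only by phone (at most 80–90% of the cohort on the protocol's expectation). Serious second-day events can still come to light.

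The number of events missed cannot be estimated, because the documents give no frequency for reactions starting at 24 to 48 hours. The prevalence analysis and the sample size are unaffected. The conclusion assumes that participants receive no instruction beyond section 3.4. It takes no position on which of the two periods is right.

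**What to change.** Reconcile sections 3.3 and 3.4 so that the period for which participants are asked to report reactions is the same as the period in which adverse events are recorded, and carry that period into the participant instructions. The cost is protocol and participant-instruction wording. No extra visit is needed.
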